7.3. Additional Statistical Considerations

7.3.1. Descriptive Statistics

Univariate descriptive statistics and frequency distributions will be calculated, as appropriate for all variables. Baseline values for demographic, clinical, and outcome variables (primary and secondary) will be tabulated for the enrolled participants. These summaries will be summarized for the overall sample and by Fitzpatrick Skin Type.

7.3.2. Handling of Missing Data

Missing data may occur throughout the study. The primary analysis, which is based on the AI and human interpretation of the images relative to the in-person assessment, will require that all test site regions have an interpretation of the reaction grade. If missing data is not able to be obtained by re-assessing the data, a “worst case” imputation strategy will be used. With this missing data will be included in the denominator of test sites tested but none of the regions will be included in the numerator for measurement of accuracy or concordance between AI and human interpretation (i.e., is counted as a “miss” in the analysis). For demographic and medical history data, any missing data will be reported as such in the final analysis.

7.3.3. Multiplicity

There will be no adjustment to the level of significance for multiple testing. All results will be reported unadjusted at the alpha=0.05 level of significance using estimates and 95% confidence intervals.

7.3.4. Interim Analysis

There is no planned interim analysis.

7.3.5. Analysis Sets

The analysis set for this study will follow the modified intention to treat principle. To be included in the analysis, the participant needs to be randomized and complete at least the day 5 assessment (final documentation of the skin reactions). Participants that study the allergen exposure challenge early are still eligible for the final analysis provided they consent to a day 5 assessment (see schedule of assessment early in the event the day 5 assessment occurs earlier).

8. Safety and Adverse Events

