1.3.2. Study #2: Prospective Clinical Trial (IRB 21-011596)

A prospective, pragmatic clinical trial was designed to advance the technologies associated with a democratized skin patch testing approach that leveraged novel patch designs and an integrated smartphone-based application to capture and upload photographs of the patch testing sites to the cloud. The study incorporated an in person, clinical assessment at all three study visits to establish the reference criterion according to current clinical protocol. Photographs were captured at each visit to provide means to evaluate a novel deep learning model for the detection of allergic contact dermatitis. While the deep learning algorithm's performance could be established relative to the in-clinic reference reading, it was unknown just how well a human reader could function when only exposed to the photographs of the test sites (i.e., not able to palpate suspicious regions). To address this, the study incorporated a human reading protocol where the same photographs, void of any data collected about the patient or information obtained during the clinical visit, were reviewed by humans to determine what the accuracy of the machine learning approach in the context of human readers.

A total of 232 participants consented to participate and 206 reached the day five assessment. A specific purpose of this study was to enroll 50% of participants with Fitzpatrick Skin Types IV – VI. This objective was achieved as the distribution of skin types over the six types were as follows: 46.6% were classified as types IV-VI. The mean (SD) participant age was 39.1 (13.5) years, and 66% (136/206) of the participants were female. A total of 32.0% (66/206) of participants self-identified as being Black or African American, 16.5% (34/206) as Asian (34/206), and 40.3% as White (83/206). A total of 23 participants self-identified as Other (11.2%) or of Hispanic origin (73.9%, 17/23).

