4.4.2. Data Collection and Follow-up for Withdrawn Subjects

Participation is strictly voluntary. The participant will be followed according to protocol to document the reactions if the participant is willing. If the participant is unable or unwilling to continue with protocol procedures, the study records will be noted as such.

5. Test Patch and Allergen Details

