7.2.2. Secondary Study Endpoints

- The accuracy for the classification of the test site region using a 5-point scale: Grades 0 – 4.
- Sensitivity
- Specificity
- False positive rate
- False negative rate
- Percentage early termination of testing
- Percentage of participants that removed patches early
- Adverse events related to allergen exposure
- Patient feedback on the testing process

Primary Hypothesis:

The AI algorithm will provide non-inferior performance measured by binary classification accuracy relative to the human performance.

To test the primary hypothesis, The primary hypothesis to be tested is the “agreement” between the clinical (in person) evaluation and the human review and AI predictions of the app captured images. Generalized estimating equations (GEE) will be structured to estimate the clustered accuracy using an identity link and robust variance estimator to account for the clustering within the database. The model will have a single predictor that indicates which reader (AI vs. human) is associated with the accuracy determination (a 1/0 with 1 indicating the “reader” reached the same conclusion as the expert, in person review). For the purpose of the primary outcome measure, the prediction from either the human or AI algorithm will be dichotomized into no reaction (grade 0) vs. any reaction (grades 1 – 4). The estimate and 95% CI for the “reader” effect will summarize the differential performance between the human and AI interpretations. For the AI algorithm to be considered non-inferior, a limit of inferiority of 5 percentage points will be used. The fitted model will be used to estimate the overall performance and 95% CI for the two readers. As shown in the figure, we desire both the human and AI performance to provide greater than 95% accuracy.

To supplement this analysis, the area under the receiver operating characteristic curve (AUC ROC) will be computed using the visual analog scale by test site determined by the human observer and the AI model’s output. DeLong’s test will be used to compare the differences in performance between these two approaches.

Secondary Hypothesis 1:

For the secondary endpoint of agreement on the 5 point clinical scale, unweighted and weighted Kappa will be used to estimate the degree to which the human and AI interpretations agree. The unweighted analysis will focus on the direct match on grade assigned to each of the test sites.

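### The only analysis set requires a Day 5 assessment, so patched participants who withdraw without one fall outside the early-termination and early-removal percentages, and possibly the adverse-event summary

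*Combined protocol and SAP*

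**What the plan says.** Section 7.3.5 names a single population: "The analysis set for this study will follow the modified intention to treat principle". Its entry condition is "To be included in the analysis, the participant needs to be randomized and complete at least the day 5 assessment". The next sentence makes one allowance: those who stop the exposure early "are still eligible for the final analysis provided they consent to a day 5 assessment", and a parenthesis contemplates that this assessment may take place ahead of schedule. No safety set or all-patched set appears anywhere in the document.

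Section 7.2.2 includes among its secondary endpoints "Percentage early termination of testing", "Percentage of participants that removed patches early" and "Adverse events related to allergen exposure". None has a stated denominator. The safety paragraph later in the same section says that adverse events will be tabulated at study level, split into allergen-related and protocol-related, and names no population.

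Section 4.4.1 allows withdrawal at any time and foresees a patch being taken off early because of a possible reaction. Section 4.4.2 continues follow-up for those who are willing. For the rest: "If the participant is unable or unwilling to continue with protocol procedures, the study records will be noted as such".

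**The concern.** Three of the secondary endpoints describe people whose testing did not go as intended. The only defined analysis set selects people whose testing got as far as a Day 5 assessment. Someone who is patched, reacts, takes the patch off and declines to come back is a case for early removal, probably a case for early termination, and possibly an adverse event. The same person fails the entry condition.

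Selection into the set can therefore depend on the outcome being counted. Section 1.2.2 treats the allergens as investigational agents, and the Study Summary gives the aim as supporting fully remote patch testing. How often exposed participants stop, remove the patch or have an adverse event matters to anyone reading the results with that aim in mind.

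**Working it through.** The plan states no figure for these endpoints, so there is nothing to reproduce. The check has two parts: which participants the wording reaches, and how far the percentages could move.

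**Who is in and who is out, reading the sections together**

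- Stops exposure early, has a Day 5 assessment: in the set (7.3.5).
- Removes the patch early, has a Day 5 assessment: in the set. Section 5.5 has the removal documented at the Day 3 visit.
- Patched, then withdraws with no Day 5 assessment: outside the set (7.3.5), with the withdrawal noted in the records (4.4.2).
- Adverse event in that last participant: to be recorded, since sections 8.1 and 8.2 cover all events from patch application to Day 5. Whether it is tabulated depends on whether the safety paragraph of 7.2.2 or the set in 7.3.5 governs, and the document does not say.
- The worst-case rule in 7.3.2 is written for missing test-site interpretations in the primary analysis. It does not return anyone to these three endpoints.

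**How many could be outside**

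Input, section 1.3.2: "A total of 232 participants consented to participate and 206 reached the day five assessment".

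- Loss from consent to Day 5: (232 − 206)/232 = 26/232 = 11.2% (exact 95% CI 7.5% to 16.0%).
- Applied to the 150 adaptive-study participants (3.2), as an assumption: 150 × 0.112 = 16.8, about 17, leaving 133. For the 100 in Phase 1: about 11.

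The 11.2% starts from consent. The document does not say how many of the 26 had a patch applied, so 17 is on the high side for participants who were patched and then lost.

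**How far a percentage could move**

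Let C be patched participants with a Day 5 assessment, of whom x are cases, and L be patched participants without one, of whom y are cases.

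- Plan's set: x/C
- All patched: (x + y)/(C + L)

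The plan's figure is too low exactly when y/L exceeds x/C.

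Illustration for early removal, with x = 6 assumed (the documents give no rate). The second column takes the upper-side loss of 17. The third takes 9, about half of it, to allow for people lost before patching.

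| Share of those lost who are cases | L = 17, C = 133: plan's set 6/133 = 4.5% | L = 9, C = 141: plan's set 6/141 = 4.3% |
|---|---|---|
| None | 6/150 = 4.0% | 6/150 = 4.0% |
| A quarter | 10.25/150 = 6.8% | 8.25/150 = 5.5% |
| Half | 14.5/150 = 9.7% | 10.5/150 = 7.0% |
| All | 23/150 = 15.3% | 15/150 = 10.0% |

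If nobody lost was a case, the plan's set slightly overstates the percentage. If cases are more common among those lost, it understates it. For early termination the last row is the relevant one if leaving before Day 5 counts as termination, because then every lost participant is a case. Section 7.2.2 does not define the term.

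**The case against.** The strongest reply is that an unstated denominator is not a stated exclusion. Sections 8.1 and 8.2 require every adverse event to be recorded whether or not the participant attends Day 5, the Schedule of Events also marks an adverse-event assessment at the off-study evaluation, and section 7.2.2 tabulates events without reference to the Day 5 set. This stands for adverse events: a reader might infer that they are certainly lost from the summary, and the documents do not support that. It does not settle the matter, since recording an event does not define an analysis population. For the two percentage endpoints there is no comparable wording.

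A reader might also infer that everyone who stops early is dropped. That is wrong, because section 7.3.5 keeps those who agree to a Day 5 assessment. For the same reason early termination is not forced to 0%: some participants can end exposure early and still be counted. What remains is narrower. Being kept depends on willingness to be assessed.

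The size can be challenged too. The 11.2% counts from consent, and the documents give no adverse-event, early-removal or early-termination rate, so no specific corrected percentage can be supported. Underestimation is likely but not proved. These points stand.

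Finally, the three endpoints are descriptive, no hypothesis is tested on them, and no objective in section 2 names tolerability. The primary analysis compares readers with the in-person Day 5 reading, so requiring that reading there is appropriate. This limits the severity but does not remove the gap.

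**Conclusion.** The point holds in this form. The single set in section 7.3.5, applied as written, leaves patched participants without any Day 5 assessment out of the early-termination and early-removal percentages. Their place in the adverse-event summary is unclear because sections 7.2.2 and 7.3.5 can be read differently. This is more than a missing detail: following the stated rule can give a wrong percentage.

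The percentages are likely to be too low, on the assumption that people with troublesome reactions are less willing to return. If return is unrelated to the reaction, early removal and adverse events are not biased. The size is unknown. About 17 of 150 is an upper-side guide to the number affected, and it assumes that the prior trial's loss carries over and that all of it came after patching. The table values are illustrations and not estimates.

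Severity is moderate. The primary accuracy comparison and the sample size are untouched.

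**What to change.** In section 7.3.5:

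- Add a safety set of all participants with at least one test patch applied, reported by phase, with the pilot shown separately if it is included.
- Name it as the denominator for adverse events, early termination and early patch removal, and refer to it in the safety paragraph of section 7.2.2.
- Report the number in this set without a Day 5 assessment, and note that their adverse-event data may be incomplete.
- State that the Day 5 requirement applies only to the accuracy and agreement analyses.

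The cost is about a paragraph of text, with no change to the sample size or visits. The protocol already calls for withdrawals, early removals and adverse events to be recorded. The new set corrects the denominator but cannot guarantee a complete numerator, since early removal is documented at a Day 3 visit that a withdrawn participant may miss and follow-up after withdrawal depends on willingness. The reported tolerability figures may look slightly less favourable.

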8.1. Definitions

Unanticipated Problems Involving Risk to Subjects or Others (UPIRTSO)

Any unanticipated problem or adverse event that meets the following three criteria:

- Serious: Serious problems or events that results in significant harm, (which may be physical, psychological, financial, social, economic, or legal) or increased risk for the subject or others (including individuals who are not research subjects). These include: (1) death; (2) life threatening adverse experience; (3) hospitalization - inpatient, new, or prolonged; (4) disability/incapacity - persistent or significant; (5) birth defect/anomaly; (6) breach of confidentiality and (7) other problems, events, or new information (i.e. publications, DSMB reports, interim findings, product labeling change) that in the opinion of the local investigator may adversely affect the rights, safety, or welfare of the subjects or others, or substantially compromise the research data, **AND**
- Unanticipated: (i.e., unexpected) problems or events are those that are not already described as potential risks in the protocol, consent document, not listed in the Investigator's Brochure, or not part of an underlying disease. A problem or event is "unanticipated" when it was unforeseeable at the time of its occurrence. A problem or event is "unanticipated" when it occurs at an increased frequency or at an increased severity than expected, **AND**
- Related: A problem or event is "related" if it is possibly related to the research procedures.

Adverse Event

An untoward or undesirable experience associated with the use of a medical product (i.e., drug, device, biologic) in a patient or research subject.

Serious Adverse Event

Adverse events are classified as serious or non-serious. Serious problems/events can be well defined and include;

- death
- life threatening adverse experience
- inpatient hospitalization or prolongation of existing hospitalization
- persistent or significant disability or incapacity
- substantial disruption of the ability to conduct normal life functions
- birth defect/congenital anomaly

and/or per protocol may be problems/events that in the opinion of the sponsor-investigator may have adversely affected the rights, safety, or welfare of the subjects or others, or substantially compromised the research data.

All adverse events that do not meet any of the criteria for serious, should be regarded as **non-serious adverse events**.

Adverse Event Reporting Period

Adverse events that occur between the time of the test patch application (Day 1) and Day 5 should be reported on the study CRFs.

Preexisting Condition

A preexisting condition is one that is present at the start of the study. A preexisting condition should be recorded as an adverse event if the frequency, intensity, or the character of the condition worsens during the study period.

General Physical Examination Findings

At screening, any clinically significant abnormality should be recorded as a preexisting condition. At the end of the study, any new clinically significant findings/abnormalities that meet the definition of an adverse event must also be recorded and documented as an adverse event.

Post-study Adverse Event

All unresolved adverse events should be followed by the sponsor-investigator until the events are resolved, the subject is lost to follow-up, or the adverse event is otherwise explained. At the last scheduled visit, the sponsor-investigator should instruct each subject to report, to the sponsor-investigator, any subsequent event(s) that the subject, or the subject's personal physician, believes might reasonably be related to participation in this study.

Hospitalization, Prolonged Hospitalization or Surgery

Any adverse event that results in hospitalization or prolonged hospitalization should be documented and reported as a serious adverse event unless specifically instructed otherwise in this protocol. Any condition responsible for surgery should be documented as an adverse event if the condition meets the criteria for an adverse event.

8.2. Recording of Adverse Events

At each contact with the subject, the study team must seek information on adverse events by specific questioning and, as appropriate, by examination. Information on all adverse events should be recorded immediately in the source document, and also in the appropriate adverse event section of the case report form (CRF). All clearly related signs, symptoms, and abnormal diagnostic, laboratory or procedure results should be recorded in the source document.

All adverse events occurring during the study period must be recorded. The clinical course of each event should be followed until resolution, stabilization, or until it has been ultimately determined that the study treatment or participation is not the probable cause. Serious adverse events that are still ongoing at the end of the study period must be followed up, to determine the final outcome. Any serious adverse event that occurs during the Adverse Event Reporting Period and is considered to be at least possibly related to the study treatment or study participation should be recorded and reported immediately.

8.3. Reporting of Serious Adverse Events and Unanticipated Problems

When an adverse event has been identified, the study team will take appropriate action necessary to protect the study participant. The sponsor-investigator will evaluate the event and determine the necessary follow-up and reporting required.

8.3.1. Sponsor-Investigator reporting: notifying the Mayo IRB

The sponsor-investigator will report to the Mayo IRB any UPIRTSOs and Non-UPIRTSOs according to the Mayo IRB Policy and Procedures.

8.3.2. Sponsor-Investigator reporting: Notifying the FDA

The sponsor-investigator will report to the FDA all unexpected, serious suspected adverse reactions according to the required IND Safety Reporting timelines, formats, and requirements.

Unexpected fatal or life threatening suspected adverse reactions where there is evidence to suggest a causal relationship between the study drug/placebo and the adverse event, will be reported as a serious suspected adverse reaction. This will be reported to the FDA-on-FDA Form 3500A, no later than 7 calendar days after the sponsor-investigator's initial receipt of the information about the event.

Other unexpected serious suspected adverse reactions where there is evidence to suggest a causal relationship between the study drug/placebo and the adverse event, will be reported as a serious suspected adverse reaction. This will be reported to the FDA-on-FDA Form 3500A, no later than 15 calendar days after the sponsor-investigator's initial receipt of the information about the event.

Any clinically important increase in the rate of serious suspected adverse reactions over those listed in the protocol or product insert will be reported as a serious suspected adverse reaction. This will be reported to the FDA-on-FDA Form 3500A no later than 15 calendar days after the sponsor-investigator's initial receipt of the information about the event.

The sponsor-investigator must also notify the FDA (and sponsors must notify all participating investigators) in an IND safety report of potential serious risks, from clinical trials or any other source, as soon as possible, but in no case later than 15 calendar days after the sponsor determines that the information qualifies for reporting under § 312.32(c)(1)(i)-(iv).

Findings from other studies in human or animals that suggest a significant risk in humans exposed to the drug will be reported. This will be reported to the FDA-on-FDA Form 3500A, no later than 15 calendar days after the sponsor-investigator's initial receipt of the information about the event.

8.4. Unmasking/Unblinding Procedures

In the event of a reaction to one of the allergens, the primary medical professional performing the in-person evaluation will have access to the unblinding information (i.e., identification of the allergens for each test site). The cause of any reactions will be denoted in the study records and communicated to the participant.

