3.4. Identification of Source Data

Study-specific case report forms (CRFs) will be used to document all of the following:

1. Demographics and medical history including assessment of Fitzpatrick skin types
2. Patient will be assigned to one of the randomized allergen templates that will be used for the study.
3. Documentation of the randomized location of the allergens on the test patch used with the participant
4. Documentation of the reference criterion (in person assessment by medical professional with training in patch testing Day 5) as well as the initial impression of reactions at Day 3 immediately following the removal of the patches.
5. Participant feedback on the user experience of the test patching
6. Documentation of the blinded human review of the photographs acquired on Day 3 and Day 5
7. Adverse events

The following source data will not be directly collected in the CRFs, but will be integrated into the master database:

- Test site photographs
- AI predictions on the photographs

4. Subject Selection Enrollment and Withdrawal

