6.2. Visit 2 (Day 3)

Participant will be asked to return after 48 hours (Day 3) for patch removal and preliminary reaction assessment.

Skin will be assessed and documented for reactions which may include irritation, redness, and/or swelling localized to the patch test area.

The reaction will be documented as negative, irritation, or positive contact allergic reaction using the scale described below in section 6.6.

Participant will be encouraged to let the study team know if there was any itching or burning while the patches were in place.

A complete set of photos will be taken to document any reactions with the smart phone application and other camera systems.

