6.3. Visit 3 (Day 5)

After about 96 hours (Day 5), the participant will return for a final assessment.

This assessment time is the final (reference criterion) assessment as it is necessary to allow for up to five days for a skin reaction to appear.

At the visit, the medical professional with training in patch testing will review the skin for any reaction and document in the CRF.

A complete set of photos will be taken to document the reactions using the smart phone application and other camera systems.

Participant feedback on the patch testing experience will be documented.

Severe contact dermatitis will be treated with topical steroids if needed.

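### Section 8.4 lets the in-person reader see the allergen key after a reaction, with no rule that the Day 5 reference grades be recorded first

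*Combined protocol and SAP*

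**What the plan says.** The trigger for opening the key is given in Section 8.4: "In the event of a reaction to one of the allergens". No visit is named. In that event, "the primary medical professional performing the in-person evaluation will have access to the unblinding information". The access covers "identification of the allergens for each test site", so it is not confined to the well that reacted. The section adds: "The cause of any reactions will be denoted in the study records and communicated to the participant". It sets no timing for this either.

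There are two in-person readings. Under Section 6.2 participants "return after 48 hours (Day 3) for patch removal and preliminary reaction assessment", and at that visit "The reaction will be documented as negative, irritation, or positive contact allergic reaction". Section 3.4 lists the reference criterion as source data "as well as the initial impression of reactions at Day 3 immediately following the removal of the patches". Of the Day 5 reading, Section 6.3 says: "This assessment time is the final (reference criterion) assessment". Footnote d of the Schedule of Events confirms this.

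Section 5.6 masks the person who reads the photographs to allergen location, in-person findings and AI output, and delays that reading by at least a month. It says nothing about the in-person reader.

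**The concern.** The AI and the human photo reader are both scored against the Day 5 in-person grades, and neither has the allergen key. If the person setting those grades knows which allergen sits in each well, expectation can enter the standard itself.

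The primary cut is sensitive to this. Section 7.2.1 counts grade 1 and above as a reaction, and Section 6.6 makes grade 1 a doubtful reaction showing faint erythema only. The endpoint therefore turns on doubtful versus negative, which is a call that depends heavily on judgement.

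The plan evidently regards allergen knowledge as a source of bias. It randomises allergen positions, hides them from the photo reader and imposes a washout. A section headed as unmasking also presupposes that the in-person reader starts masked, although no section says so.

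The secondary kappa comparing allergens alone and in combination (Section 7.2.2) is exposed in a similar way. A reader who grades both arms with the key open knows which combination well holds an allergen that has already reacted on the primary patch.

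**Working it through.** There is no stated figure to reproduce. The check is of the order of events, followed by arithmetic for scale only.

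**Order of events**

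1. Day 3, about 48 hours: patches come off and reactions are graded (6.2). A reaction recorded here meets the 8.4 trigger.
2. From then on, 8.4 permits access to the identity of every well. It contains no condition about grades still to be recorded.
3. Day 5, about 96 hours: the reference grades are recorded (6.3). No section masks this reader, requires someone other than the Day 3 reader, or locks the grades before the key is opened.
4. Hence, following the text as written, the reference can be graded about 96 − 48 = 48 hours after the key became available.

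**Scale**

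Inputs: 100 Phase 1 participants (3.1), 10 primary wells each (5.2.1), and a 5-point non-inferiority limit on accuracy (7.2.2).

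- Sites: N = 100 × 10 = 1,000.
- One changed reference grade moves one reader's accuracy by 1/1,000 = 0.1 percentage point. Ten changes move it by at most 10 × 0.1 = 1 point.
- Where the AI and the human photo read agree, a changed reference grade moves both accuracies equally and their difference by 0.
- Where they disagree, one gains 0.1 and the other loses 0.1, so the difference moves by 2/1,000 = 0.2 point.
- Moving the difference by the full 5-point limit would need a net 5/0.2 = 25 changes in one direction, all at sites where the two reads disagree.

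The documents give no rate at which knowledge of the key changes a grade, so these are conversion factors and not estimates of bias.

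**How many participants could be affected**

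The quantity needed is the proportion with a reaction visible on Day 3, which the documents do not give. The chance of at least one reaction at any time, treating wells as independent, depends on the rate used:

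- The ten percentages in 5.2.1, read as positivity rates: 1 − 0.486 = 51%.
- The 6.4% found at Day 5 in the prior trial (1.3.2): 1 − 0.936^10 = 48%.
- The 15% site rate in 7.1: 1 − 0.85^10 = 80%.

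None of these is a Day 3 figure, and 6.3 itself allows up to five days for a reaction to appear.

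**The case against.** **Early opening is allowed only by silence.** Section 8.4 does not mention Day 3, and its provisions on recording the cause and telling the participant fit the final visit equally well. Section 6.2 does not say who grades on Day 3, so the eventual Day 5 reader need not be the person who opened the key. This stands, and it limits the point to what the plan permits; it does not show that early opening will happen.

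**The reference is routine practice.** The Study Summary defines it as expert in-person review as done in standard operations. That may explain the access, but it does not protect the grades, and locking them first leaves the examination unchanged.

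**The primary comparison is partly insulated.** AI and human photo reads share one reference, so their difference is affected only where they disagree. This is correct, and it is why the exposure lies mainly in the absolute accuracies.

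**The key is not the only leak.** Section 5.3 uses four placement sequences assigned consecutively, allots the combination patch by odd or even study number, and describes no randomised positions for its four wells. An attentive reader might infer much without the key. This also stands, and a lock does not cure it.

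Three stronger readings are tempting but not supported:

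- A reader might infer that one unmasked assessor grades both arms and that the kappa is therefore inflated. No section assigns readers to arms, so the kappa could be raised if that happens, and no more can be said.
- A reader might infer that about half of the reference readings would be unmasked. The 51% and 48% figures are chances of any reaction. They are neither a Day 3 rate nor an upper bound, as the 80% shows.
- A reader might infer that irritant versus allergic calls decide the dichotomy. Section 6.6 gives irritant reactions no number on the 0 to 4 scale, so this cannot be established.

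**Conclusion.** The gap is real. As written, the plan allows the Day 5 reference to be graded by someone who already knows the allergen in every well, and it does not record whether that occurred. This could shift doubtful-versus-negative calls and hence both absolute accuracies, including the aim of exceeding 95%. The AI-minus-human difference is less exposed. The kappa for allergens alone versus in combination could be raised if one unmasked reader grades both arms.

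The conclusion rests on the absence of any timing rule in 8.4 or masking rule for the Day 5 reader, and on the possibility that the Day 5 reader has seen the key. The size and direction of any bias, and the share of participants with a Day 3 reaction, cannot be derived from the documents. The point does not show that the trial's results would be wrong. It identifies an unprotected step that is cheap to close beforehand and, if openings are not logged, cannot be reconstructed afterwards.

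**What to change.** - In Sections 8.4 and 6.3, state that Day 5 grades for all wells on both arms are entered and locked before the key is opened.
- Where the investigators judge earlier access necessary for a participant's care, log its date, time and reason, and reconcile 8.4 with this rule.
- Report the number of participants unmasked before Day 5 and describe results by unmasking status. This status depends on having reacted. Excluding these participants would preferentially remove positive sites and change accuracy even with no expectation bias, so such an analysis cannot isolate the bias and should not be presented as doing so.

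The cost is a sentence in each section and a time stamp on the CRF. The downside is a possible short delay in telling participants which allergen they reacted to. The lock does not remove the guessability that comes from the consecutive sequences and the odd/even patch assignment in 5.3, and the report should acknowledge that limit.
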